#### **7.6.1 Deaths**

See Core Safety SAP.

#### **7.6.2 Serious Adverse Events**

See Core Safety SAP.

#### **7.6.3 Adverse Events Leading to Discontinuation of Study Therapy**

See Core Safety SAP.

#### **7.6.4 Adverse Events Leading to Dose Delay of Study Therapy**

See Core Safety SAP.

#### **7.6.5 Adverse Events**

See Core Safety SAP.

#### **7.6.6 Select Adverse Events**

See Core Safety SAP.

#### **7.6.7 Immune Modulating Medication**

See Core Safety SAP.

#### **7.6.8 Multiple Events**

See Core Safety SAP.

## **7.6.9 Clinical Laboratory Evaluations**

### **7.6.9.1 Hematology**

See Core Safety SAP.

### **7.6.9.2 Serum Chemistry**

See Core Safety SAP.

### **7.6.10 Immunogenicity**

See Core Safety SAP.

### **7.6.11 Vital Signs and Pulse Oximetry**

See Core Safety SAP.

## **7.7 Pregnancy**

See Core Safety SAP.

## **7.8 Pharmacokinetics**

Summary statistics will be calculated for nivolumab and ipilimumab concentrations, and summarized by scheduled sample collection time. The nivolumab concentration data obtained in this study will be combined with data from other studies in the clinical development program to develop a population PK model. This model will be used to evaluate the effects of intrinsic and extrinsic covariates on the PK of nivolumab. In addition, exposure-response analyses with selected efficacy and safety endpoints will be conducted. Results of population PK and exposure-response analyses will be reported separately.

[REDACTED]

[REDACTED]

[REDACTED]

[REDACTED]

[REDACTED]

[REDACTED]

- [REDACTED]
- [REDACTED]

[REDACTED]

[REDACTED]

- [REDACTED]
- [REDACTED]
- [REDACTED]

[REDACTED]

- [REDACTED]
- [REDACTED]

[REDACTED]

- [REDACTED]
- [REDACTED]

[REDACTED]

- [REDACTED]

[REDACTED]

- [REDACTED]
- [REDACTED]

[REDACTED]

- [REDACTED]
- [REDACTED]

[REDACTED]

- [REDACTED]

[REDACTED]

- [REDACTED]
- [REDACTED]

[REDACTED]

- [REDACTED]

medium, high)

CI for median OS in each treatment group will be computed via the log-log transformation

[REDACTED]

## 8 CONVENTIONS

The following conventions may be used for imputing partial dates for analyses requiring dates:

For missing and partial adverse event onset dates, imputation will be performed using the Adverse Event Domain Requirements Specification. Missing and partial Non-Study Medication Domain dates will be imputed using the derivation algorithm described in 4.3.3 of BMS Non-Study Medication Domain Requirements Specification.

For death dates, the following conventions will be used for imputing partial dates:

- If only the day of the month is missing, the 1st of the month will be used to replace the missing day. The imputed date will be compared to the last known date alive day and the maximum will be considered as the death date.
- If the month of the year is missing, the death date will be imputed as the last known date alive day.
- If the date is completely missing but the reason for death is present, the death date will be imputed as the last known date alive day.

For date of progression, the following conventions will be used for imputing partial dates:

- If only the day of the month is missing, the 1st of the month will be used to replace the missing day\*.
- If the day and month are missing or a date is completely missing, it will be considered as missing.

\*In cases where the date of death is present and complete, the imputed progression date will be compared to the date of death. The minimum of the imputed progression date and date of death will be considered as the date of progression.

For other partial/missing dates, the following conventions may be used:

- If only the day of the month is missing, the 15th of the month will be used to replace the missing day.
- If both the day and the month are missing, “July 1” will be used to replace the missing information.
- If a date is completely missing, it will be considered as missing.

The following conversion factors will be used to convert days to months or years: 1 month = 30.4375 days and 1 year = 365.25 days.

Duration (e.g. time from first diagnosis to first dosing date, duration of response, and time to response) will be calculated as follows:

$$\text{Duration} = (\text{Last date} - \text{first date} + 1)$$

All statistical analyses will be carried out using SAS (Statistical Analysis System software, SAS Institute, North Caroline, USA) unless otherwise noted.

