## 4 ENDPOINTS

### 4.1 Primary

#### 4.1.1 Objective Response Rate

The primary endpoint is the objective response rate (ORR). The ORR is defined as the number of subjects with a best overall response (BOR) of complete response (CR) or partial response (PR) divided by the number of treated subjects. The BOR is defined as the best response designation, as determined by the investigator or BICR, recorded between the date of treatment assignment and the date of objectively documented progression per RECIST 1.1 or the start date of subsequent anti-cancer therapy, whichever occurs first. CR or PR determinations included in the BOR assessment must be confirmed by a second scan no less than 4 weeks after the criteria for response are first met. For subjects without documented progression or subsequent therapy, all available response designations will contribute to the BOR assessment. For subjects who continue treatment beyond progression, the BOR should be determined based on response designations recorded up to the time of the initial RECIST 1.1-defined progression.

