Progression free survival (PFS) is defined as the time from first dosing date to the date of the first documented progression, as determined by the investigator or BICR (per RECIST 1.1), or death due to any cause, whichever occurs first. Subjects who die without a reported progression or start of any subsequent anti-cancer therapy will be considered to have progressed on the date of their death. Subjects who did not progress or die will be considered as not progressed and will be censored on the date of their last evaluable assessment or last evaluable assessment prior to crossover. Subjects who did not have any on study assessments and did not die will be censored on the first dosing date. Subjects who started any subsequent anti-cancer therapy without a prior reported progression will be censored at the last evaluable assessment prior to initiation of the subsequent anti-cancer therapy. Please refer to Table 4.2-1 for the censoring scheme in primary analysis of PFS.

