**Table 4.2-1: Censoring scheme used in primary analysis of PFS**

Situation	Date of Progression or Censoring	Outcome
No baseline tumor assessments and no death	First dosing date	Not Progressed
No on study tumor assessments and no death	First dosing date	Not Progressed
Progression documented between scheduled visits	Date of the first documented tumor progression per RECIST 1.1	Progressed
Clinical progression without evidence of progression per RECIST 1.1 or No progression	Date of last tumor assessment with no documented progression or last evaluable assessment prior to crossover (for crossover subject without PD)	Not Progressed

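### Partial progression dates are set to the 1st of the month with no lower bound, so an imputed progression can precede the first dose or a same-month scan without progression

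*SAP*

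**What the plan says.** Section 8 (Conventions) carries the same rule in SAP version 2.0 and in the SCLC expansion SAP. For a progression date with only the day missing, "the 1st of the month will be used to replace the missing day". A footnote applies when the date of death is complete: "The minimum of the imputed progression date and date of death will be considered as the date of progression".

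The rule for partial death dates, just above it, uses the same 1st-of-month start but adds a floor: "The imputed date will be compared to the last known date alive day and the maximum will be considered as the death date".

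The progression date then feeds three definitions:

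- **PFS** (section 4.2): "Progression free survival (PFS) is defined as the time from first dosing date to the date of the first documented progression". The censoring table gives the event date as "Date of the first documented tumor progression per RECIST 1.1" and adds no check against earlier dates.
- **DOR** (section 4.2): ends at the first documented progression or death.
- **Best overall response, BOR** (section 4.1.1): designations count up to "the date of objectively documented progression per RECIST 1.1 or the start date of subsequent anti-cancer therapy, whichever occurs first". A response must be confirmed by a second scan at least 4 weeks later.

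Section 8 computes durations as last date minus first date plus 1.

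**The concern.** The check on an imputed progression date guards the side on which the rule does not err. If progression occurred on or before death, the 1st of the progression month cannot be later than death. The minimum then simply returns the imputed date, and the footnote acts only when the recorded dates already conflict. The rule can only be too early, and nothing limits that.

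Taken literally, the rule can date progression before treatment began, or before a scan that showed no progression. A Kaplan-Meier analysis has no place for a negative time, so someone would have to repair or exclude such a subject by an unplanned decision. In the response analysis, an early progression date could shut out a scan that was in fact done before progression. ORR is the primary endpoint, so that route matters most if it occurs.

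**Working it through.** The plan gives no figure for this point, so there is none to reproduce. The check is date arithmetic.

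**Inputs.** Missing day set to 1 (section 8); duration = last - first + 1 (section 8); PFS origin = first dose (section 4.2); confirmation at least 28 days after response criteria are first met (section 4.1.1). The SAPs do not give the scan interval or the number of partial dates, so a range of gaps is shown.

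**Size of the shift.** A true date on day d of the month moves back d - 1 days, from 0 to 31 - 1 = 30. Over every date in 2016-2017 the mean is 14.7 days.

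**When the order reverses.** Let an earlier event (first dose or scan) lie k days before true progression. The imputed date precedes it only if both fall in the same calendar month. Taking every true progression date in 2016-2017:

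| k (days) | imputed date precedes the event (duration zero or negative) | duration negative |
|---|---|---|
| 7 | 74% | 70.5% |
| 14 | 51% | 47.5% |
| 21 | 28% | 24.5% |
| 28 | 5% | 1.9% |
| 30 or more | 0% | 0% |

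These are shares of partial dates with that gap, not of subjects.

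**PFS.** First dose 10 March, progression recorded as March: 1 - 10 + 1 = -8 days. The section 8 formula does not name PFS among its examples; without the +1 the result would be -9. If progression comes 42 days after the first dose, PFS cannot fall below 13 days.

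**BOR.** Partial response 5 February, confirmed 8 March (more than 28 days later), true progression 28 March recorded as March. The imputed date is 1 March. If the window closes there, the 8 March scan is outside it and the response is unconfirmed. With the planned arms of 150 and 100, one lost responder is 1/150 = 0.7 or 1/100 = 1.0 percentage points.

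**DOR.** Counted from the date criteria were first met, with confirmation at least 28 days later and progression after that, progression comes at least 29 days after the start. The largest shift is 30 days, so the minimum is 29 - 30 + 1 = 0. Counted from the confirmation scan on 8 March, DOR would be 1 - 8 + 1 = -6, but only if BOR had not been cut at 1 March. If it had been cut, there is no response and no DOR.

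**The case against.** The strongest reply is that the situation is narrow. It needs a missing day and an earlier event in the same calendar month, at most 29 days before progression. The PFS example needs progression within 21 days of the first dose, and the BOR example needs scans 20 days apart. Progression rests on RECIST assessments, since clinical progression alone is not an event, and nothing suggests that such dates often lack a day. This stands, and it keeps the point minor. It does not remove it: the censoring table itself foresees progression between scheduled visits.

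Second, section 8 opens permissively: "The following conventions may be used for imputing partial dates for analyses requiring dates". However, the sentence that introduces the progression rule is mandatory, so a programmer would apply it as written.

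Third, the earliest possible date is a conservative choice applied alike in both arms, and PFS and DOR are only estimated by arm. That defends the 1st of the month as a starting value. It does not defend a date that contradicts a dated scan or the first dose.

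Fourth, the BOR window can be read by scan order, because the text speaks of documented progression and never says that an imputed date overrides an earlier dated scan. This stands: loss of a confirmed response depends on the reading chosen.

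A reader might also infer that DOR goes negative. It does not when DOR starts at the date criteria were first met. Section 4.2 can be read as starting at confirmation, but then a negative DOR and a lost response are alternatives for one subject, never both.

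**Conclusion.** The gap is real and minor. Followed as written, the progression rule can give zero or negative PFS, or progression dated before a scan without progression, whenever the earlier event shares its calendar month. Whether a confirmed response can be lost depends on closing the BOR window at the imputed date, which the SAPs neither state nor exclude.

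The shift is 0 to 30 days, about 15 on average if true dates are spread evenly over the month. Reversal is impossible at gaps of 30 days or more. The number of partial progression dates is not given, so no effect on ORR or PFS can be quantified; it is probably small. The documents do not support the inference that the primary comparison is biased, or that every partial date is moved: a true date on the 1st is unchanged.

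**What to change.** In section 8 of both SAPs, replace the progression rule for a missing day with this derivation:

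1. Take the later of the 1st of the reported month and the day after the last evaluable on-study non-progression assessment that precedes the reported progression in visit order. If there is no such assessment, use the first dosing date in its place.
2. Do not let the result pass the end of the reported month.
3. Take the earlier of that and the date of death.

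State that assessments after the reported progression are not used. Without that limit, a later scan during treatment beyond progression, which both SAPs allow for, could push the date forward and lengthen PFS.

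In the examples, PFS with a first dose on 10 March becomes 10 - 10 + 1 = 1 day. With the confirmatory scan on 8 March, progression is dated 9 March and the confirmed response is kept under either reading of the BOR window.

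The cost is one sentence per SAP and a short change to the derivation code. Complete dates are unaffected. The visit at which progression was reported must be identifiable.

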## **9 CONTENT OF REPORTS**

All analyses described in this SAP will be included in the Clinical Study Report(s) except where otherwise noted. Refer to the Data Presentation Plan for mock-ups of all tables and listings.
